**Screening Nutritional Status of Hospitalized Patients With
Nutritional Risk Screening 2002 and Subjective Global
Assessment Tools**

Document Date: December 1, 2016

Materials and methods

Participants

The study was conducted with 134 adult patients (male/female: 59/75) who were hospitalized in the clinics (hematology, neurology, gastroenterology, nephrology, endocrine, pulmonary disease and cardiology) of Malatya Training and Research Hospital between January 1 and August 30, 2016.

The exclusion criteria included: patients were (i) < 18 years old, (ii) hospitalized due to surgical operation, (iii) pregnant women, (iv) breastfeeding women, (v) bed-dependent, (vi) suffered an advanced disease that required palliative care.

The study was approved by the Ethics Committee of [removed for blind peer review]. A written informed consent was obtained from the patients.

Study design

In the cross-sectional study demographic data (age, gender), BMI, cause of hospitalization and hospital LOS were recorded. For the nutritional assessment all patients were screened with NRS 2002 and SGA within the first days of admission to the patients. And also the edema and the acid were evaluated by the physician. The primary predictors of interest in our study were the NRS 2002 and SGA results of patients.

In the beginning 168 patients were included to study but, 34 patients did not complete scanning process by the reason of missing data and excluded from the study. Finally 134 patients completed the nutritional scanning (Fig.1).

BMI classification

BMI as an objective measurement, refers to the weight for height, which is valid for both genders and all age groups. BMI classification according to WHO refers to, <16,5 kg/m² severe malnourished, 16,5-18,5 kg/m² malnourished, 18,5-24,9 kg/m² normal, 25-29,9 kg/m² overweight, ≥30 kg/m² obese in adults ⁽⁹⁾. ESPEN recognises malnutrition as, patient has (i) weight loss > % 10 – 15 of body weight in last 6 months; (ii) BMI < 18,5 kg/m²; (iii) level B and C (mild-to-moderate and severe malnourished) according to SGA or score ≥3 according to NRS 2002; (iv) serum albumin < 30 g/L (out of hepatic and renal dysfunction) ⁽¹⁰⁾.

Nutritional status

Nutritional status of all patients were screened both NRS 2002 and SGA within the first days of admission to the patients.

The patients were classified as being nutritionally risk (NRS+): total score ≥ 3 or nutritionally risk-free (NRS-): total score < 3 according to NRS 2002 results.

The SGA screening normally provides three alternative categories for nutritional classification: well nourished (A); mild-to-moderately malnourished (B); or severely malnourished (C).

In order to facilitate the analysis of the influence of the nutritional status on the outcomes, to allow comparison with the NRS 2002 and SGA, patients were grouped as being either non-malnourished (A) or malnourished (B or C; included mild-to-moderately malnourished and severely malnourished according to SGA results). And according to the results of two screening tools, patients were grouped as being malnourished [included patients on (NRS+) or SGA (B or C)] and non-malnourished [included patients on (NRS-) or SGA (A)].

Statistics

The sample size was calculated as minimum 88 patients based on the primary outcome variable: the detection of a 5% difference between the nutritional status and NRS 2002 and SGA tools and statistical power of 95%. Continuous variables were expressed as the mean and standard deviation. Statistical differences between groups were assessed using Chi-Square and Fisher exact tests for categorical variables, while the Student's t-test was used for continuous variables. In order to analyze which variables affected the prevalence of malnutrition, a logistic regression analysis was performed, in which malnutrition according to the NRS 2002 and SGA was considered the dependent variable separately. The level of significance used was 0.05. Statistical analysis was carried out with IBM SPSS Statistics 22.0.

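### NRS 2002 ≥3 is defined as nutritional risk but grouped and modelled as malnutrition, and the combined grouping rule, read as one rule, puts discordant patients in both groups

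*Combined protocol and SAP*

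**What the plan says.** All references are to the combined protocol and SAP.

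- **Nutritional status, NRS definition.** "The patients were classified as being nutritionally risk (NRS+): total score ≥ 3", set against "nutritionally risk-free (NRS-): total score < 3 according to NRS 2002 results". Both labels speak of risk.
- **Nutritional status, SGA definition.** SGA yields a graded state in three levels (A, B, C). For analysis it is cut in two: "patients were grouped as being either non-malnourished (A) or malnourished (B or C".
- **Nutritional status, grouping sentence.** The rule reads: "patients were grouped as being malnourished [included patients on (NRS+) or SGA (B or C)] and non-malnourished [included patients on (NRS-) or SGA (A".
- **Logistic regression, in Statistics.** "malnutrition according to the NRS 2002 and SGA was considered the dependent variable separately".
- **BMI classification, cited definition.** A list introduced by "ESPEN recognises malnutrition as, patient has" contains, as item (iii), SGA level B or C "according to SGA or score ≥3 according to NRS 2002". The other items are weight loss, BMI below 18.5 kg/m² and serum albumin below 30 g/L. The text does not say whether one item is enough or all are needed, nor that the study uses the list as its own definition.

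**The concern.** The study compares two tools, so what each positive result means has to be fixed. By the plan's own definitions, NRS ≥3 flags risk and SGA B or C grades a state. If both are then called malnutrition, a prevalence of malnutrition by NRS is, on the plan's definition, a prevalence of risk. Variables said to affect the prevalence of malnutrition in the NRS model are likewise variables associated with risk. Some disagreement between the tools may then reflect a difference in what they are defined to measure.

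This bears on the main question, because the sample-size statement gives as primary outcome a difference involving nutritional status and the two tools.

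The grouping sentence adds a separate problem. If it describes one grouping built from both tools, its two categories overlap, and a patient with discordant results has no unique place.

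**Working it through.** The plan states no figure on this point, so there is none to reproduce. The check is a comparison of definitions, followed by simple algebra on the grouping rule.

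**Step 1: the label at each place of use.**
- NRS definition (Nutritional status): NRS ≥3 is risk.
- Grouping sentence (Nutritional status): NRS+ is malnourished.
- Regression outcome (Statistics): the NRS result is malnutrition.
- Cited ESPEN list (BMI classification): NRS ≥3 appears as a criterion of malnutrition.

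The cut-off is the same throughout and only the meaning changes. The cited list is the one possible bridge. The plan does not state that it is adopted, and the grouping uses item (iii) alone, although Study design says BMI was recorded and BMI is another item on the list.

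**Step 2: the grouping sentence taken as one rule.** Let the 134 analysed patients fall into four cells:
- a: NRS+ and SGA B or C
- b: NRS+ and SGA A
- c: NRS− and SGA B or C
- d: NRS− and SGA A

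Malnourished (NRS+ or SGA B/C) = a + b + c.

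Non-malnourished (NRS− or SGA A) = b + c + d.

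Sum of the two groups = (a + b + c + d) + (b + c) = 134 + (b + c).

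Every discordant patient is counted twice. The groups are exclusive only if b + c = 0.

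**Step 3: what the label does not change.** NRS+ prevalence is (a + b)/134 and SGA B/C prevalence is (a + c)/134. Their difference is (b − c)/134. None of these depends on the word used, and the same holds for the chi-square and Fisher tests and for the two separate logistic models.

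**Step 4: illustrations, on assumed inputs only.** The documents give no NRS+ count, no SGA B/C count and no cross-table.
- An either-tool group exceeds the SGA B/C group by b. If b is 5% of patients, 0.05 × 134 = 6.7, about 7. If b is 20%, 0.20 × 134 = 26.8, about 27.
- Suppose NRS+ is 40% and SGA B/C is 30%. The either-tool group lies between max(0.40, 0.30) = 40% and 0.40 + 0.30 = 70%, that is 0.40 × 134 = 53.6 to 0.70 × 134 = 93.8, or about 54 to 94 patients.
- On the same assumption the discordant share lies between 0.40 − 0.30 = 10% and 70%, that is 13.4 to 93.8 patients. By Step 2 the two literal groups would add up to between 147.4 and 227.8 in a study of 134.

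**The case against.** The strongest defence is that the relabelling has a cited source. The ESPEN list comes before any grouping and names SGA B/C or NRS ≥3 together as a criterion, which the grouping sentence mirrors. A tool-specific name for a score band and a working definition with the same cut-off need not conflict. This stands in part: the switch is not unexplained. What remains is that the plan never says it adopts the list, leaves the other criteria unused, and gives its own definition of NRS+ as risk.

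Second, the grouping sentence can be read tool by tool (NRS+ against NRS−, B/C against A). That reading is coherent, fits the stated aim of comparing the tools, and agrees with the regression, which models them separately. No analysis of a combined group is named in Statistics. This also stands, so pooling is one reading and not an established fact. The sentence is nevertheless worded as a single grouping from both results, and on either reading NRS+ is called malnourished.

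Third, the regression outcome is attributed to the tool and the cut-off is explicit, so a careful reader can see what was counted. That is true, and it limits the harm to interpretation.

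Fourth, reserving the word malnourished for SGA would make SGA the arbiter, although the plan calls both instruments screening tools and names no reference standard. This stands as a caution: discordance should not be charged to either tool.

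**Conclusion.** The point holds as an unreconciled double definition and an ambiguous grouping rule. NRS ≥3 means risk where it is defined and malnutrition where it is grouped and modelled. Read as one combined grouping, the rule puts NRS+/SGA A and NRS−/SGA B or C patients in both groups.

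The effect is on the meaning of the NRS prevalence and the NRS model, and on who belongs to any combined group. Per-tool counts, tests and coefficients stay as they are.

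A reader might infer more: that the plan reports risk as disease, that it pools the tools in its analysis, or that malnutrition prevalence is inflated by 7 to 27 patients. The documents do not support these. They contain no results, the label has a cited if unadopted basis, and the regression keeps the tools apart. The 7 to 27 figure is an illustration that applies only to an either-tool group with an assumed 5% to 20% of patients NRS+ but SGA A. With the tools kept separate, the difference in prevalence is (b − c)/134, which could have either sign.

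**What to change.** 1. Name the NRS outcome nutritional risk (NRS ≥3) in the grouping, the regression and all prevalence reporting. If the ESPEN label is used anywhere, say so explicitly, state whether one criterion or all are required, and explain why the others are not applied.
2. Report the prevalence of NRS risk and of SGA B/C separately.
3. Replace the combined group with the cross-table of NRS risk by SGA category. If a combined group is kept, make its categories exclusive, with non-malnourished requiring both NRS− and SGA A.
4. Describe NRS+/SGA A patients as discordant. Do not present them as an error of either tool, since no reference standard is named.

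The cost is relabelling and one table from data already collected on the 134 patients. The downside is that a single headline prevalence of malnutrition, from NRS or from the combined group, is no longer quoted.

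### The claim that 88 patients give 95% power for a 5% difference cannot be reproduced, and 88 falls short of 95% if the 5% means percentage points between NRS 2002 and SGA

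*Combined protocol and SAP*

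**What the plan says.** The only sample-size justification is one sentence in the Statistics section. It opens with the number and the effect: "The sample size was calculated as minimum 88 patients based on the primary outcome variable: the detection of a 5% difference". Its remainder names the comparison and gives the power, in per cent, as follows: "between the nutritional status and NRS 2002 and SGA tools and statistical power of 95". Later in the same section: "The level of significance used was 0.05".

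Three other statements bear on what is being compared.

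- Study design: "all patients were screened with NRS 2002 and SGA within the first days of admission". A comparison between the tools is therefore within patient.
- Nutritional status: NRS 2002 is split at a score of 3, and SGA is reduced to two classes by merging its two malnourished grades: "to allow comparison with the NRS 2002 and SGA, patients were grouped as being either non-malnourished (A) or malnourished".
- Study design also says: "The primary predictors of interest in our study were the NRS 2002 and SGA results of patients".

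The planned tests are for groups: "Statistical differences between groups were assessed using Chi-Square and Fisher exact tests for categorical variables". For the rest, Student's "t-test was used for continuous variables". No paired test is named, and none of these tests is tied to the sample-size sentence. Of 168 patients included, 34 were excluded for missing data and 134 were analysed.

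**The concern.** A sample-size statement should let a reader recover the number. This one gives four figures (88, 5%, 95%, 0.05) and leaves out everything else. It does not say clearly which two quantities differ by 5%, or whether the 5% is in percentage points, relative or standardised.

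The reading best supported by the design is a paired difference of 5 percentage points in the proportion classed as malnourished. A difference that small at 95% power normally needs far more than 88 patients.

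The stake is interpretation, since recruitment is over. A reader who trusts the sentence could take a non-significant difference between NRS 2002 and SGA as good evidence that the tools agree to within 5 points.

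**Working it through.** **Inputs from the document.** N = 88 (minimum), difference 5%, power 95%, alpha 0.05, both tools on every patient, both dichotomised, 134 analysed. **Assumed, because not given:** the scale of the 5%, test, sidedness, discordance, prevalence, standard deviation.

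**1. Reproducing 88 by the usual paired formula.** With d = 0.05 and discordant proportion pd,

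N = [z_alpha × sqrt(pd) + z_beta × sqrt(pd − d²)]² / d².

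A 5-point difference needs pd of at least 0.05. At that minimum, two-sided:

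N = [1.96 × sqrt(0.05) + 1.645 × sqrt(0.0475)]² / 0.0025 = 254 (one-sided: 211).

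At pd = 0.10 it is 514 (428), and at pd = 0.20 it is 1034 (861). None is near 88.

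**2. Enumerated power in the best case.** Let all discordance run one way. The number of discordant pairs X is then binomial(N, 0.05), and each test rejects once X reaches a threshold.

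- Uncorrected McNemar: the statistic equals X. Two-sided needs X ≥ 4 (4 > 3.84); one-sided needs X ≥ 3 (sqrt(3) = 1.73 > 1.645).
- Exact McNemar: two-sided needs 2 × 0.5^X ≤ 0.05, so X ≥ 6; one-sided needs 0.5^X ≤ 0.05, so X ≥ 5.
- Likelihood ratio: G = 2X ln 2. Two-sided needs X ≥ 3 (4.16 > 3.84); one-sided needs X ≥ 2 (2.77 > 2.71).

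For example, P(X ≥ 4 | 88, 0.05) = 1 − (0.011 + 0.051 + 0.116 + 0.175) = 0.647.

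| Test, best case, n = 88 | Two-sided | One-sided |
|---|---|---|
| Uncorrected McNemar | 64.7% | 82.2% |
| Exact McNemar | 27.7% | 45.1% |
| Likelihood ratio (anti-conservative here) | 82.2% | 93.8% |

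The smallest N reaching 95% in this best case is 153 two-sided or 124 one-sided (uncorrected), and 208 or 181 (exact).

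**3. With some reverse discordance.** Full enumeration over discordant counts, difference fixed at 5 points, two-sided, exact to uncorrected:

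| Assumed discordance | n = 88 | n = 134 |
|---|---|---|
| 5%, all one way | 28–65% | 67–91% |
| 10% | 20–30% | 35–44% |
| 20% | 13–18% | 19–26% |
| 30% | 9–14% | 15–18% |

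One-sided at 10% discordance: 30–45% at n = 88 and 48–59% at n = 134.

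**4. Other readings of the 5%.**

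- Relative 5%: never more than 5 points. At an assumed 40% prevalence it is 0.05 × 40 = 2 points, with best-case uncorrected power of 10% two-sided or 26% one-sided.
- Unpaired, 88 ratings per tool, Pearson: 65% two-sided or 82% one-sided at 0% vs 5%; 23% or 36% at 5% vs 10%; 11% or 17% at 30% vs 35%. Fisher at 0% vs 5%: 28% or 45%.
- 88 patients split into two groups, 0% vs 5%, Pearson, best split: 60% two-sided (70/18) or 69% one-sided (65/23).

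**5. Where a number near 88 does arise.**

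- Two-sample t-test, one-sided, standardised effect 0.5: 88 per group is the smallest size reaching 95% (95.14%, against 94.95% at 87). That is 2 × 88 = 176 patients.
- Precision of ±5 points at 95% confidence: 1.96² × 0.061 × 0.939 / 0.05² = 88, so prevalence of about 6%. At 30% prevalence it is 323. This is precision, not power.
- Paired mean difference of 5 units: needs a standard deviation of about 13 two-sided (5/0.389) or 14 one-sided (5/0.353).
- One-sample test against a fixed rate of roughly 0.1–0.5%.

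Each needs an input that the document does not contain, and none is a 5-point difference between the tools with 88 patients in total.

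**The case against.** The strongest reply is that the sentence never says the 5% is a paired difference between NRS 2002 and SGA. It speaks of nutritional status and the tools, the tools are called predictors, and every planned test is between groups. This stands: the paired reading is a judgement from the design, and the power figures depend on it. It does not rescue the sentence, because the Pearson and Fisher readings of 5 points fail too and the missing inputs remain missing.

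A reader might infer that 65% and 82% are ceilings for any test. They are not. They belong to the uncorrected McNemar test (and to Pearson in the unpaired version). The likelihood-ratio test goes higher, though still below 95% at n = 88.

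A reader might also infer that the calculation was wrong, or that the power claim is knowingly false. The document shows no calculation, so this cannot be established. The exact match at 88 per group for a standardised effect of 0.5 is equally compatible with a sound calculation transcribed badly.

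Finally, 134 patients exceed the stated minimum, and the document reports no comparison of the tools and draws no conclusion from a null result. That is fair, and it makes the harm prospective. Nor does the larger sample fail in every case: with no reverse discordance, the one-sided uncorrected test reaches 97% at n = 134, as does the two-sided likelihood-ratio test, since both reject at X ≥ 3. That extreme requires every patient flagged by one tool to be flagged by the other as well.

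**Conclusion.** The firm part is that the combination of 88 patients, 5% and 95% cannot be reproduced from what the document states. The conditional part is that, read as 5 percentage points between the two dichotomised tools, 88 patients do not give 95% power under any test tried, one- or two-sided, even at the most favourable discordance. With realistic reverse discordance the shortfall is large. The 10%, 20% and 30% discordances are illustrations, since the document gives no basis for choosing among them.

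This should be fixed because it is the study's only sample-size justification. It affects what may be concluded from a non-significant difference between the tools. It does not show that the study was wrongly conducted or that more patients are needed.

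**What to change.** State the calculation behind 88: the comparison, scale of the 5%, test, sidedness, assumed rates or discordance (or standard deviation), and whether 88 is a total or per group. If that is unavailable, say so and withdraw the claim of 95% power for a 5-point difference between NRS 2002 and SGA.

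Report the 2x2 table of NRS 2002 by SGA for the 134 patients and the paired difference with its 95% CI, and do not read a non-significant result as excluding 5 points. This does not repair the sentence, but it replaces an unsupported power claim with the precision achieved. For orientation, at a true difference of 5 points the half-width is 1.96 × sqrt((discordance − 0.05²)/134), or 5.3, 7.5 and 9.2 points at assumed discordances of 10%, 20% and 30%. Any such figure, or any detectable difference quoted, must be labelled as resting on an assumed discordance.

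The cost is one reworded sentence and one small analysis on data already collected, with no new patients. The stated figure becomes less favourable.

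### All 134 patients were rated with both NRS 2002 and SGA, but no listed method can validly test or estimate the within-patient difference between the tools

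*Combined protocol and SAP*

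**What the plan says.** Both ratings exist for every analysed patient. Study design states that "all patients were screened with NRS 2002 and SGA within the first days of admission to the patients" and closes with "Finally 134 patients completed the nutritional scanning". The Nutritional status section repeats that "Nutritional status of all patients were screened both NRS 2002 and SGA".

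NRS 2002 is split at a score of 3, and SGA is reduced to A versus B or C. The reason given for the SGA grouping is "In order to facilitate the analysis of the influence of the nutritional status on the outcomes, to allow comparison with the NRS 2002 and SGA".

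Statistics bases the minimum of 88 patients on "the detection of a 5% difference between the nutritional status and NRS 2002 and SGA tools and statistical power of 95" per cent, and calls this the primary outcome variable. The methods listed there are means and standard deviations, the t-test for continuous variables, and for the rest: "Statistical differences between groups were assessed using Chi-Square and Fisher exact tests for categorical variables". Logistic regression follows, in which "malnutrition according to the NRS 2002 and SGA was considered the dependent variable separately". The section names no McNemar test, paired difference in proportions, kappa or percentage agreement.

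**The concern.** Two binary ratings on the same patients are paired data. Whether one tool labels more patients as malnourished than the other depends only on the patients whom the tools classify differently. No listed method uses that information.

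- Chi-Square or Fisher on the two prevalences treats one set of 134 patients as two independent samples.
- Chi-Square or Fisher on the NRS-by-SGA table tests whether the ratings are associated. A small p-value there shows neither a difference in prevalence nor good agreement.
- The two logistic models take the tools as separate outcomes and never contrast them.

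A comparison for which the SGA grouping was at least partly made therefore has no valid estimate or test in the text. If one of the listed tests were used to fill the gap, the conclusion could be wrong in either direction.

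**Working it through.** The documents give n = 134, both tools on every patient, and a significance level of 0.05. They give no prevalence, no discordance (the share of patients classified differently) and no kappa. All such values below are assumptions, and the tables are invented.

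**1. The plan's own figure.** The only calculated figure in Statistics is the minimum of 88. A two-sided McNemar calculation for a 5-point paired difference at 95% power, with discordance at its smallest possible value of 5%, gives n = [1.96·√0.05 + 1.645·√(0.05 − 0.05²)]² / 0.05² = 254. The smallest two-sided unpaired result (0% versus 5%) is 251 per group. The figure 88 is not reproduced, so it does not reveal which contrast was meant. That is a separate sample-size issue, and nothing below depends on it.

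**2. Ignoring the pairing.** Take both positive 40, NRS+ only 12, SGA B/C only 2, both negative 80.

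- Prevalences: 52/134 = 38.8% and 42/134 = 31.3%; difference 10/134 = 7.5 points.
- Unpaired Chi-Square: pooled proportion 94/268 = 0.351; SE = √(0.351 × 0.649 × 2/134) = 0.0583; z = 0.0746/0.0583 = 1.28; p = 0.20.
- Exact McNemar: 14 discordant patients, split 12 to 2; p = 2 × (1 + 14 + 91)/2¹⁴ = 0.013.

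More generally, if both tools have prevalence p, the variance of the difference is 2p(1−p)/n when the pairing is ignored and 2p(1−p)(1−κ)/n when it is respected. The unpaired standard error is therefore too large by a factor 1/√(1−κ): 1.20 at κ = 0.3 and 1.58 at κ = 0.6.

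**3. Testing association instead.** Take 30/27/20/57 in the same cell order.

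- Chi-Square = 134 × (30×57 − 27×20)² / (57×77×50×84) = 9.95; p = 0.0016.
- Yet 27 + 20 = 47 of the 134 patients are classified differently. Observed agreement is 87/134 = 0.649, chance agreement is (57×50 + 77×84)/134² = 0.519, and kappa is (0.649 − 0.519)/(1 − 0.519) = 0.27.
- Exact McNemar gives p = 0.38.

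The same pattern appears on average. With both prevalences 35% and kappa 0.3, discordance is 2 × 0.35 × 0.65 × 0.7 = 0.3185, or about 43 of 134 patients. In 400,000 simulated samples Chi-Square on the cross-table rejected in 93%, although prevalence is equal and agreement is poor.

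**4. What a paired analysis would deliver.** The Wald half-width is 1.96 × √((discordance − 0.05²)/134), for a true difference of 5 points.

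| Assumed discordance | 95% CI half-width (points) |
|---|---|
| 5% | 3.7 |
| 10% | 5.3 |
| 18% | 7.1 |
| 25% | 8.4 |

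The first row is rough, because only about 0.05 × 134 ≈ 7 discordant patients are expected. For kappa, simulated standard errors of 0.086 (κ = 0.3) and 0.073 (κ = 0.6) give half-widths of 1.96 × SE = 0.17 and 0.14.

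**The case against.** The strongest reply is that a head-to-head comparison of the tools is not clearly an objective. Study design calls the two tools' results the main predictors. The first reason given for the SGA grouping is the influence of nutritional status on outcomes, and the regressions are run separately by tool. On that reading the study is two parallel analyses, each comparing different patients, and the listed tests suit it. The wording about allowing comparison is also unclear, and could mean comparing other variables with each tool's result.

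Much of this stands. The listed tests are appropriate for malnourished versus non-malnourished patients, and no listed analysis is invalidated. Agreement is nowhere declared as an aim, so kappa is a suggestion and its absence is not in itself a defect. The reply does not remove the point, however. The grouping sentence and the sample-size sentence both involve the two tools in a comparison or difference. If the listed tests serve only comparisons between different patients, nothing at all is listed for the tools.

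A reader might infer that Chi-Square was in fact applied to the NRS-by-SGA table or to the two prevalences. The text does not say so, and steps 2 and 3 of the working show a risk, not something known to have happened. A reader might also infer, from the grouping that combines both tools, that each tool was tested against a classification built from itself. The text defines that grouping but reports no such test.

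**Conclusion.** The omission is real and should be fixed; the finding is limited to that. The data are paired, a comparison involving the tools is signalled, and no listed method can validly test or estimate the within-patient difference. That much rests on the text and on no assumed figure. The size of the consequence does rest on assumptions. In the invented tables the choice of test moves p from 0.20 to 0.013, or yields a significant association while about a third of patients (47 of 134) are classified differently.

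It would go too far to say that the primary outcome has no valid analysis. The 5% sentence is too ambiguous to establish that the paired difference is the primary outcome. Nor does this point show that the study is too small: power for a 5-point difference is a separate matter.

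**What to change.** - State which contrast the 5% in the sample-size sentence refers to.
- For NRS+/− versus SGA A/(B or C), report the paired 2x2 table, the paired difference in proportions with a 95% CI, and a McNemar test. Name the variant used (exact or mid-p).
- Label this analysis as added after data collection. Patients were hospitalised from January to August 2016 and the document is dated December 2016, so it cannot be presented as pre-specified.
- Optionally, give Cohen's kappa with a 95% CI as a descriptive measure of agreement.
- Keep Chi-Square, Fisher and the t-test for comparisons between different patients, and say which comparison each one serves.
- Rest the interpretation on the confidence interval, and say that a non-significant McNemar result is not evidence that the tools agree.

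The cost is one extra cross-table analysis on existing data and a few sentences. The drawback is limited precision: with an interval of roughly ±4 to ±8 points under the assumed discordances, the analysis may well not resolve a 5-point difference.

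### Student's t-test is the only test named for continuous variables, although nothing controls the nutritional group sizes; Welch's test would be a cheap safeguard for age and BMI, and LOS needs a separate decision

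*Combined protocol and SAP*

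**What the plan says.** The Statistics section gives one method for continuous data, Student's test: "t-test was used for continuous variables". The summary is likewise on the raw scale: "Continuous variables were expressed as the mean and standard deviation". On the threshold it says "The level of significance used was 0.05", without stating whether tests are one- or two-sided.

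Under Study design, "demographic data (age, gender), BMI, cause of hospitalization and hospital LOS were recorded". The continuous variables among these are age, BMI and LOS.

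The groups to be compared come from the screening itself. NRS 2002 is split at a total score of 3. For SGA, "patients were grouped as being either non-malnourished (A) or malnourished (B or C" and so on. The analysed total is given ("Finally 134 patients completed the nutritional scanning"), but not how many patients fell on each side of either tool. No Welch version, transformation or rank test is mentioned, and no SD is reported.

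**The concern.** Student's t-test estimates one common variance. That is harmless when the groups are equal in size or the spreads are equal. When both differ, the standard error is wrong in a predictable direction. It is too small if the smaller group is the more variable one, and too large if the smaller group is the less variable one.

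Here the group sizes follow from a cutoff or a classification, so a 67/67 split would be a coincidence. At stake are the p-values and intervals for age, BMI and, by inference, LOS between nutritional groups. The chi-square and Fisher tests and the logistic regressions are not touched.

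**Working it through.** **Inputs from the documents.** N = 134; significance level 0.05 (taken as two-sided); Student's t-test. Group sizes and SDs are not given, so the splits 54/80, 40/94 and 27/107 (prevalence about 40%, 30% and 20%) and SD ratios of 0.5 to 2 are assumptions.

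**Formula.** With n1 the smaller group, the large-sample true error of the pooled test is

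2 × [1 − Φ(1.96 × √(Vp/Vt))], where

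- Vp = {[(n1−1)s1² + (n2−1)s2²]/(N−2)} × (1/n1 + 1/n2), the variance the pooled test assumes;
- Vt = s1²/n1 + s2²/n2, the true variance of the difference.

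**The plan's own figure.** If s1 = s2, or if n1 = n2, then Vp = Vt and the error is 5%, as stated.

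**Worked case: 40/94, SD ratio 1.5** (s1² = 2.25, s2² = 1):

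- pooled variance = (39 × 2.25 + 93 × 1)/132 = 1.369
- Vp = 1.369 × (1/40 + 1/94) = 0.0488
- Vt = 2.25/40 + 1/94 = 0.0669
- √(Vp/Vt) = 0.854; 1.96 × 0.854 = 1.674; error = 9.4%

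**All cases, normal data** (formula, with simulation of 100,000 datasets per setting in brackets):

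| Split | Smaller group has half the SD | 1.5 times | 2 times |
|---|---|---|---|
| 67/67 | 5.0% (5.0%) | 5.0% (4.9%) | 5.0% (5.1%) |
| 54/80 | 2.8% (2.8%) | 6.9% (6.9%) | 8.2% (8.2%) |
| 40/94 | 1.2% (1.3%) | 9.4% (9.5%) | 12.7% (12.5%) |
| 27/107 | 0.4% (0.5%) | 12.2% (12.1%) | 18.0% (17.9%) |

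With equal SDs the simulated error was 5.0% at every split in the table. Welch's test stayed at 4.9-5.1% in all these normal-data settings.

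**Cost of Welch if the SDs are equal** (true difference 0.5 SD): power 74.3% against 74.9% at 40/94 (0.6 points), and 62.1% against 63.7% at 27/107 (1.6 points). Other runs gave 0.3-1.3 points.

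**LOS, treated as log-normal (an assumption).**

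- *Same distribution in both groups* (log SD 0.6-0.8): the pooled test on raw days rejects 4.6-5.1% of the time and raw Welch 4.7-6.8%. Skewness alone therefore does not invalidate the pooled test at this N.
- *Smaller group stays 1.35 times longer, common log SD*: the raw SD is then also 1.35 times larger. The pooled 95% interval for the difference in mean days misses the truth 7.6-8.2% of the time at 40/94 and 9.4-9.7% at 27/107. Raw Welch misses 5.8-7.5%. Welch on log LOS misses 4.9-5.1%, but its target is the ratio of geometric means.
- *Equal mean days, 40/94, SD ratio 1.5-2*: Welch on log LOS rejects 15-54% of the time, because geometric means then differ although mean days do not.
- *Skewed raw data (log SD 0.8), SD ratio 1.5*: raw Welch has an error of 6.6% at 40/94 and 8.0% at 27/107, against 9.3% and 11.7% for the pooled test.

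**The case against.** The strongest reply is that this describes a possibility and not a demonstrated error. That stands. The harm needs both unequal sizes and unequal spreads, and the documents show neither for the nutritional groups. The only split they state is by sex, 59/75; there the pooled error would be 6.2% and 6.9% at SD ratios of 1.5 and 2. The documents give no reason why age or BMI should differ in spread that much.

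A reader might infer that the comparisons have wrong error bars whichever group is more variable. The documents do not support this, since with similar SDs or near-equal groups the pooled test is sound. A reader might also infer that skewed LOS by itself breaks the test, or that Welch holds 5% whatever the data. The LOS results above contradict both. Nor is log-scale Welch a repair of the comparison of mean days: it answers another question. Its power advantage over the raw pooled test (about 1-9 points in the log-normal model) comes from the transformation. Raw Welch in that model had less power than the pooled test (62% against 69%, and 32% against 44%, at 40/94).

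On wording, the pooled variance is implied by the test's name and is not written out. The text reports past analyses, and LOS is covered only through the general sentence on continuous variables. SPSS also prints the unequal-variance row, so the text does not settle which row was read. This last point argues for naming the row: left open, it can be chosen after both p-values are seen.

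**Conclusion.** The point holds as a conditional weakness of low severity. A test sensitive to unequal spread is named for groups whose sizes the design does not control. For normal data the true error could lie anywhere from about 0.5% (27/107, smaller group with half the SD) to about 18% (27/107, smaller group with twice the SD). It stays at 5% if the SDs are equal or the split is 67/67. These figures rest on assumed splits and SD ratios, and the documents do not show where in the range this study falls. The case for change is the asymmetry: Welch costs at most about 1.6 power points in the settings tried if it was not needed, and removes the exposure for roughly normal variables if it was. For LOS no single test does everything, so the target of the comparison has to be chosen and stated.

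**What to change.** **Age and BMI.** In the Statistics section, replace Student's test with Welch's unequal-variance t-test, used in every case and without a preliminary variance test. This is one sentence; SPSS already prints the result, and existing data can be re-analysed. Report group sizes and SDs for each comparison so that a reader can judge how much it matters.

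**LOS, as a separate change.** Describe it by median and interquartile range. If a test is wanted, use Welch's test on log LOS and give the ratio of geometric means with a 95% confidence interval. State that this compares geometric means rather than mean days, and that it does not control the error rate for a comparison of mean LOS. The cost is this change of estimand: the result is a ratio and no longer a difference in days. If mean days is the quantity of interest, the log-scale test should not stand in for it, and raw Welch should be described as approximate for skewed data.
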